3.1.5. Additional statistical considerations

Method for handling confounding by indication

Because this trial is observational, there may be incomplete overlap in covariates between the MHP and usual care cohorts. To account for this possibility, inverse probability of treatment weighting will be used. Propensity score matching of comparable subgroups will also be used and reported as a sensitivity analysis (13).

Propensity score matching works by creating samples of participants who have the same likelihood of receiving treatment. Logistic regression will be used to generate propensity scores; nearest-neighbor matching without replacement will be used for matching. Baseline confounders will be included in the propensity score model, if they are related to the likelihood of receiving treatment and the outcome. Date of first visit will not be included in the model (for reasons given in Section 3.1.1). Participants without similar propensity scores, defined as greater than a caliper width, will be excluded from this sensitivity analysis. The average treatment effect will be calculated for the included subset of similar participants.

Austin recommends a “caliper width,” defined as the difference between two propensity scores, as “equal to 0.2 of the standard deviation of the logit of the propensity score”(14). To balance the internal and external validity of this sensitivity analysis, this caliper width will be used, unless it excludes more than 20% of the sample. In that case, the caliper width will be increased until 80% of the participants are included. If this is adjustment is needed, the results using the smaller caliper width will be reported in the supplemental material. Following Austin (2011), standardized differences, QQ-plots, box plots, cumulative distribution functions, and empirical nonparametric density plots will be used to check the differences in baseline covariates between the treated and untreated samples (13).

Time-effects

For the primary models, we have chosen not to include the first appointment date as it could capture factors that affect the effectiveness of the app. During the study time frame, many outside factors could have affected the outcomes, especially due to the COVID-19 pandemic.

Because of this we will conduct a sensitivity analysis including a time effect, the date of the participant's first prenatal visit, in each model.

4. Software

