1.6. Overview of proposed analyses

EG will analyze the primary, secondary, and exploratory outcomes for the trial data. LH will generate data and run models as needed so that EG remains blinded to the identity of each cohort (see section 2.5).

The primary analyses will be multiple linear regression models estimating average treatment effects of the MHP app. Secondarily, dose-response models will be created for the primary and secondary outcomes in order to understand the moderating effects of app usage.

The primary and secondary outcomes for the study will come from electronic health record (EHR) data for trial participants. Given the source and the nature of care for women who deliver in the UPMC system, few outcome data are missing data. As such, imputation will not be used to account for missing outcome data. Instead, participants will be excluded from analyses, if their outcome data is missing for an outcome measure.

As a sensitivity analysis, propensity score matching will be used to create similar cohorts of participants, excluding participants whose propensity scores are outside the overlap in the covariate distributions for the covariates that predict downloading the MHP app (see section 3.1.5). We will calculate average treatment effects for these matched subsets of participants. Inverse probability of treatment weighting will be used as an additional sensitivity analysis to account for the potential lack of overlap in covariate distributions between the study cohorts.

2. Data analysis plan – data description

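### Inverse probability weighting is planned as the answer to incomplete covariate overlap, but the method assumes overlap and the plan adds no restriction that would supply it

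*SAP*

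**What the plan says.** SAP section 3.1.5, under confounding by indication, names the problem: "Because this trial is observational, there may be incomplete overlap in covariates between the MHP and usual care cohorts". Its next sentence names the remedy: "To account for this possibility, inverse probability of treatment weighting will be used". Section 1.6 repeats the reasoning: "Inverse probability of treatment weighting will be used as an additional sensitivity analysis to account for the potential lack of overlap in covariate distributions".

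The rules that deal with participants outside the overlap belong to the matched analysis. Section 1.6 describes matching as "excluding participants whose propensity scores are outside the overlap in the covariate distributions for the covariates that predict downloading the MHP app", and section 3.1.5 says: "Participants without similar propensity scores, defined as greater than a caliper width, will be excluded from this sensitivity analysis". If the caliper drops more than 20% of the sample, it is relaxed: "In that case, the caliper width will be increased until 80% of the participants are included".

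For the weighted analysis the plan gives no restriction to a common propensity range, no trimming or truncation, no weight diagnostics and no target population. Section 1.6 calls weighting a sensitivity analysis. Section 3.1.5 attaches that label explicitly only to matching. The primary analysis is covariate-adjusted linear regression.

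**The concern.** Weighting by the inverse of the propensity score balances measured confounders provided that every type of participant had some chance of being in either cohort. That is the overlap condition. If it holds only weakly, some participants carry large weights and precision falls. If one cohort is absent from part of the covariate space, no weight can stand in for people who are not there.

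The plan assigns the method to the condition that the method presupposes. What is at stake is how a sensitivity analysis will be read. If the weighted and regression estimates agree, a report that follows the plan would present this as evidence that limited overlap did not matter, and the analysis cannot provide that evidence. If they disagree, the cause may be the weighting itself and not the regression.

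**Working it through.** **Inputs from the SAP.** Cohorts of 7,147 and 5,197 deliveries, SD 10 days, 80% power, detectable difference 0.51 day (section 1.5); 5% significance level (section 3.1), taken as two-sided.

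**Inputs assumed.** The SAP does not say how strongly covariates separate the cohorts or how many participants lie outside the overlap. Both are varied below.

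**1. The plan's own figure.** Detectable difference = (1.960 + 0.842) × 10 × √(1/5197 + 1/7147) = 2.802 × 10 × 0.01823 = 0.511 day. The stated 0.51 day is reproduced.

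**2. Weak overlap: loss of precision.** Let the logit of the propensity score be normal with equal variance in the two cohorts. For c-statistic c, the standardized separation is d = √2 × Φ⁻¹(c). With r = (size of the other cohort)/(size of own cohort), the large-sample effective sample size as a share of own cohort is

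(1 + r)² / (1 + 2r + r² × exp(d²)).

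For the larger cohort r = 5197/7147 = 0.727; for the smaller r = 7147/5197 = 1.375. Example at c = 0.70: d² = 0.550 and exp(d²) = 1.733. The larger cohort gives 2.983/3.371 = 88%, the smaller 5.642/7.028 = 80%.

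The unadjusted standard error then grows by the ratio of √(1/ESS₁ + 1/ESS₀) to 0.01823, and the detectable difference grows with it.

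| c-statistic (assumed) | exp(d²) | Effective share, formula | Effective share, simulated | SE ratio (formula) | Detectable difference |
|---|---|---|---|---|---|
| 0.70 | 1.733 | 80% and 88% | 80-89% | 1.09 | 0.56 day |
| 0.75 | 2.484 | 67% and 79% | 67-79% | 1.18 | 0.60 day |
| 0.85 | 8.571 | 28% and 43% | 32-46% | 1.74 | 0.89 day |

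At 0.85 the simulated share exceeds the formula because the largest weights are rare and often missing from a finite sample. Typical largest weights in simulation are 10-17 at 0.70, 17-29 at 0.75 and 58-101 at 0.85.

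**3. One cohort absent: bias.** Suppose a share s of participants never downloads and delivers 10 days earlier, and the app has no effect. Let μ be the mean gestational age of everyone else. Members of this stratum are all in usual care with a propensity of 0, so each has weight 1/(1 − 0) = 1.

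- Weighted mean, MHP cohort: μ, because nobody from the stratum is there.
- Weighted mean, usual care: (1 − s) × μ + s × (μ − 10) = μ − 10s.
- Apparent effect: 10s days in favour of the app.

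This gives 0.20, 0.50 and 1.00 day for s = 2%, 5% and 10%. A simulation of 12,344 deliveries (300 replicates, logit slope 0.5 per SD of one confounder) gave 0.20, 0.50 and 1.01 days. The largest weight was only about 8, so inspecting the weights alone would not reveal the problem.

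**4. The alternatives in the same simulation.** Restricting the weighted analysis to propensity scores between 0.1 and 0.9, or using overlap weights, kept the mean error within 0.02 day in all three cases. Under weak overlap without an absent stratum (logit slope 2, c-statistic about 0.86), the SD of the estimate was 0.38 day with plain weights, 0.25 day with restriction and 0.23 day with overlap weights.

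**The case against.** The strongest reply has four parts.

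- **The consequence is limited.** Section 1.6 makes weighting an additional sensitivity analysis, and no primary or secondary conclusion rests on it. This stands.
- **The plan already has an analysis that restricts to comparable participants.** Caliper matching comes with standardized differences and density plots, and the narrower-caliper result is still reported if the caliper is widened. This largely stands, although widening to retain 80% loosens the restriction when overlap is poor. In any case it does not give the weighted analysis the property claimed for it.
- **Structural non-overlap is not indicated.** Under sections 1.3 and 1.4.1 everyone included was offered the prescription, and downloading was optional. The 5% stratum and its 10-day difference are assumptions. This stands.
- **Weighting is a legitimate tool for confounding by indication**, the title of the subsection, and an unrestricted estimate for the whole cohort complements matching. This also stands, and it is a reason to reword the purpose and not to drop the analysis.

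A reader might go further and infer that the weighted estimate will be driven by a few atypical women. The calculations do not show this: at c-statistics of 0.70 to 0.75 the ten largest weights carry only about 0.6-1.6% of a cohort's total weight. A reader might also infer that weighting cannot remove bias here at all, or that the bias has no limit. The first is strictly true only where one cohort is absent; near-violations bring mainly imprecision. The second has not been shown: the bias equals the share outside the overlap times its outcome difference.

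**Conclusion.** The stated rationale is wrong in both sections: weighting needs overlap, and the plan adds nothing to the weighted analysis that would secure it. The precision cost is modest if separation is ordinary (standard error up by about 9% at a c-statistic of 0.70 and 18% at 0.75) and large if separation is strong (about 74% at 0.85). Where a stratum has no app users, the bias is about 0.5 day under the assumed 5% and 10 days, roughly the whole difference that the study is powered to detect.

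These sizes rest on normal logit scores and assumed separation. They illustrate the mechanism and do not predict this study, whose actual overlap is unknown. The primary regression estimate is not called into question by this point. What fails is the inference that agreement between the weighted analysis and the regression shows robustness to non-overlap.

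**What to change.** In sections 1.6 and 3.1.5:

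- Describe inverse probability weighting as adjustment for measured confounding.
- For the overlap purpose, either restrict the weighted analysis to the common propensity range with a stated truncation rule, or add overlap weights (each participant weighted by the estimated probability of being in the other cohort).
- Report the maximum weight, the effective sample size per cohort and weighted standardized differences.
- State that the resulting estimate refers to the overlap population.
- State in section 3.1.5, as in section 1.6, that weighting is a sensitivity analysis.

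The cost is a few sentences and a small code change, since propensity scores are already planned. The downside is that the estimate applies only to the overlap population, a limit that the matched analysis already accepts. The unrestricted weighted estimate can be kept beside it, provided that it is not presented as a check on overlap.

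### The matching caliper in SAP 3.1.5 is defined on the propensity-score scale but sized on the logit scale; coded literally it is at least four times too wide, with a limited effect on one sensitivity analysis

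*SAP*

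**What the plan says.** All of the rule is in SAP section 3.1.5, under confounding by indication.

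- Scores come from logistic regression, and "nearest-neighbor matching without replacement will be used for matching".
- The caliper width is "defined as the difference between two propensity scores", and its size is "equal to 0.2 of the standard deviation of the logit of the propensity score".
- The exclusion rule also speaks of scores, not logits: "Participants without similar propensity scores, defined as greater than a caliper width, will be excluded from this sensitivity analysis".
- There is an override: "this caliper width will be used, unless it excludes more than 20% of the sample". Otherwise "the caliper width will be increased until 80% of the participants are included", and the result at the narrower caliper goes to the supplement.
- Standardised differences and several plots "will be used to check the differences in baseline covariates between the treated and untreated samples". No limit on imbalance is set.
- On the role of the analysis: "Propensity score matching of comparable subgroups will also be used and reported as a sensitivity analysis".

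The matching ratio, order and direction are not given.

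**The concern.** A propensity score lies between 0 and 1, and its logit is unbounded. A width computed from the SD of the logit is a number in logit units. If it is compared with a difference between two raw scores, it admits pairs that the cited rule would reject. SAP section 2.5 has one analyst build the propensity model while another runs the outcome models on the full data, so the written specification passes between two people and may well be coded as it stands.

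Two things are at stake: how much covariate imbalance stays in the matched sample, and how many participants are counted as unmatched, which is what the 20% exclusion trigger looks at.

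**Working it through.** **Inputs.** From the SAP: cohorts of 7,147 and 5,197, total 12,344 deliveries (section 1.5); caliper 0.2 × SD of the logit, nearest neighbour without replacement, 20%/80% override (section 3.1.5). The SAP gives no SD, no numerical caliper and no expected retention, so there is no plan figure to reproduce.

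**Step 1. The scale factor (no assumptions needed).** With logit(p) = ln[p/(1−p)], the derivative is 1/[p(1−p)]. Since p(1−p) is at most 0.25, the derivative is never below 4, and for any pair |difference in logit| ≥ 4 × |difference in p|.

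| p | 1/[p(1−p)] |
|---|---|
| 0.5 | 4.00 |
| 0.421 or 0.579 (cohort shares) | 4.10 |
| 0.3 or 0.7 | 4.76 |
| 0.2 | 6.25 |
| 0.1 | 11.1 |

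A pair at the limit of the literal caliper is therefore at least 4 × 0.2 = 0.8 SD of the logit apart, instead of 0.2 SD. Example: with an SD of 0.745 the width is 0.2 × 0.745 = 0.149. Read as a score difference, that is at least 4 × 0.149 = 0.596 on the logit.

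**Step 2. Balance at the unwidened caliper.** Assumed model: logit p = a + b·x, x standard normal, a set so that 7,147/12,344 are treated; greedy 1:1 matching in random order from the smaller cohort. The measure is the standardised difference of the logit. Ranges span repeat runs.

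| Raw difference | Literal caliper | Logit caliper |
|---|---|---|
| 0.30 | 0.012 | 0.001 |
| 0.40 | 0.025–0.038 | 0.002–0.003 |
| about 0.72 | 0.086–0.094 | 0.005–0.006 |
| about 0.92 | 0.131–0.135 | 0.008–0.009 |

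The literal caliper is clearly worse, but at raw 0.72 it leaves 0.094/0.72 = 13% at most, so it still removes most of the imbalance.

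**Step 3. Retention and the 20% trigger.** One-to-one matching can include at most 2 × 5,197/12,344 = 84.2%. Pair counts from one run:

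| Raw difference | Literal: pairs (share) | Logit: pairs (share) | Pairs lost |
|---|---|---|---|
| 0.40 | 5,034 (81.6%) | 4,893 (79.3%) | 3% |
| about 0.72 | 4,610 (74.7%) | 4,305 (69.7%) | 7% |
| about 0.92 | 4,320 (70.0%) | 3,881 (62.9%) | 10% |

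Share = 2 × pairs/12,344. At raw 0.40 the literal caliper stays above 80% and the logit caliper falls just below it; over six seeds the shares average 81.3% and 79.4%. Here the choice of scale decides whether the override is used. At the two stronger separations both calipers breach the limit.

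**Step 4. Balance after the override.** Widening each caliper until 80% of the whole sample is included gives:

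| Raw difference | Literal | Logit |
|---|---|---|
| 0.30 (not triggered) | 0.012 | 0.001 |
| 0.40 | 0.025 | 0.008 |
| about 0.72 | 0.195–0.222 | 0.186–0.215 |
| about 0.92 | 0.378–0.420 | 0.372–0.392 |

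From raw 0.7 upward the two scales end in nearly the same place. A separate simulation with a normal covariate score already gives about 0.06 on both scales at raw 0.5.

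**The case against.** **It may be shorthand.** The definition by score difference is a brief gloss around a quoted recommendation that itself names the logit, so the authors may intend to match on the logit. That is possible, and the harm arises only if the rule is coded literally. But the gloss is the only definition of the term, the exclusion sentence repeats the same scale, and nothing corrects it.

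**The 80% rule dominates.** Where separation is strong enough for the scale to matter much, the override widens even a correct caliper to about the same balance. This stands, and it limits the point to what step 4 shows. It does not remove it: the narrow-caliper result sent to the supplement is the only one at the recommended width, and literal coding would spoil that one.

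**Diagnostics would show poor matches.** Partly so. They are planned, but without a limit or an action attached, a residual near 0.09 could pass without comment.

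**Stronger readings the SAP does not support.** A reader might infer that the literal rule leaves much of the imbalance in place. It does not in the settings above: a caliper only caps the distance, and nearest-neighbour matching still takes the closest available partner. Larger residuals do occur in simulation, for example 24–31% of the raw difference when the 7,147 cohort is MHP and matching starts from it in random order, and more when matching proceeds from the largest score. The SAP fixes neither order nor direction, and cohort identity is blinded, so these cannot be attributed to the plan. A reader might also take matching to be the main check on confounding. The primary analysis is covariate-adjusted regression, weighting is used as well, and matching is labelled a sensitivity analysis.

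**Conclusion.** The point holds in limited form, at low severity. The mixed scales are in the text, and the factor of at least four is exact for literal coding, whatever the SD.

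The consequence is smaller than that factor suggests. The main matched result is affected only under weak to moderate separation, by about 0.01 to 0.02 in standardised difference (0.012 against 0.001 at raw 0.30; 0.025 against 0.008 at raw 0.40). Under stronger separation the error moves to the supplementary narrow-caliper result, where the residual is roughly 0.09 to 0.14 instead of under 0.01. Near raw 0.40 the scale also decides whether the 20% trigger fires.

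These sizes rest on an assumed normal score, 1:1 random-order matching from the smaller cohort, and 80% read as a share of the whole sample. The SAP states neither the separation between cohorts nor the matching order, direction or ratio.

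**What to change.** In SAP section 3.1.5, state that matching is on the logit of the propensity score with a caliper of 0.2 times the SD of that logit, and define caliper width as the difference between two logits. Word the exclusion sentence to match.

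The cost is one sentence, one setting in the matching code, and about 3% to 10% fewer pairs at the unwidened caliper (step 3). The change will not by itself bring the main matched result to a residual below 0.01 under strong separation, because the 80% inclusion rule governs balance there. It would help to state the matching order, direction and ratio, and a limit for standardised differences, in the same edit.

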1.5. Sample Size Justification

Due to the observational nature of the study and recruitment context, it was not possible to predetermine the sample size based on statistical power for estimating the primary and secondary outcomes. Instead, all participants who met the inclusion criteria between September 2019 and February 2022 were included. The final sample has 12,344 deliveries, divided between the MHP and usual care cohorts (with 7147 in one and 5197 in the other, with their identities currently blinded). This represents about 12,287 different participants (we only have information about the percent of multiple deliveries for participants who downloaded the app, 0.464%). Given the sample sizes in the two cohorts, there is 80% power to detect an effect size of 0.051 days. Assuming that the outcomes are normally distributed with a standard deviation of 10 days (1), the study has 80% power to detect a 0.51 day difference in gestational age at birth between the cohorts.

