3.1. Main analyses of treatment differences

The main analysis compares the mean gestational weeks at birth between the MHP and usual care cohorts. An estimate of the average treatment effect, 95% confidence interval, and effect size will be reported. EG will remain blind to the 80% of outcome data not used to set the terms of the analysis (Section 2.5).

The primary and secondary outcomes will be evaluated at the 5% significance level. No correction for chance will be used for the primary outcome, as there is only one test. For the 9 secondary outcomes, we will report both corrected and uncorrected p-values, using the Bonferroni correction to reduce risk of reporting a false positive result. As a sensitivity analysis, the Bonferroni corrected p-values for ten outcome values will be reported in the supplemental material of the report.

All tests will include all participants with data on the outcome measure involved.

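### The 20% exclusion limit that triggers caliper widening is counted on the total sample; under 1:1 matching it allows only about 5% of the smaller cohort to go unmatched, so moderate cohort separation can force a much wider caliper

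*SAP*

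**What the plan says.** SAP section 1.5 reports a total of 12,344 deliveries in two cohorts of unequal size: "with 7147 in one and 5197 in the other, with their identities currently blinded".

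Section 3.1.5 describes the matched analysis, a sensitivity analysis beside inverse probability of treatment weighting (IPTW). Scores come from logistic regression, and "nearest-neighbor matching without replacement will be used for matching". No matching ratio or matching order is given. The starting caliper is 0.2 SD of the logit of the score. It is kept unless more than 20% of the sample is excluded. Otherwise, "In that case, the caliper width will be increased until 80% of the participants are included", and the results from the narrower caliper are moved to the supplement. The section lists balance diagnostics, including standardised differences and several plots, but gives no threshold and no action if balance is poor. It also sets no maximum caliper.

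**The concern.** In matching without replacement, each member of the smaller cohort can be used once. In the 1:1 form, the surplus of the larger cohort stays unmatched whatever the caliper. Because the retention target is counted on all participants, that surplus uses up most of the 20% allowance before the caliper has excluded anyone for lack of a comparable partner.

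The caliper may therefore be widened largely because the cohorts differ in size. The cohorts here are self-selected by downloading the app, and matching is meant to compare similar women. A rule that widens the caliper further as overlap worsens, with nothing to stop it, works against that aim. What is at stake is how far the reported matched estimate can be trusted as a check on confounding.

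**Working it through.** **The plan's own figure.** Inputs from section 1.5: cohorts of 7147 and 5197; "Assuming that the outcomes are normally distributed with a standard deviation of 10 days (1"). Section 3.1 adds: "The primary and secondary outcomes will be evaluated at the 5% significance level" (taken as two-sided).

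- Detectable difference at 80% power = (1.960 + 0.842) × 10 × √(1/7147 + 1/5197) = 0.511 day.
- This agrees with the statement that "the study has 80% power to detect a 0.51 day difference in gestational age at birth between the cohorts". The cohort sizes are consistent with the plan's own power figure, and 7147 + 5197 = 12,344.

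**The cap under 1:1 matching** (ratio inferred).

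- Surplus that can never be matched: 7147 − 5197 = 1950, and 1950 / 12,344 = 15.8%.
- Maximum included: 2 × 5197 / 12,344 = 84.2%.
- Pairs needed for 80%: 0.8 × 12,344 / 2 = 4937.6, so 4938.
- Share of the smaller cohort that must be matched: 4938 / 5197 = 95.0%.
- Unmatched members allowed in the smaller cohort: 5197 − 4938 = 259, or 5.0%.

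Of the 20 percentage points of allowance, 15.8 are used by the size difference and 4.2 remain.

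**Consequence of widening (illustration).** The SAP gives no score distribution, so this part rests on assumptions: normal logit scores with equal SDs, cohort means d SDs apart, c-statistic = Φ(d/√2), and greedy 1:1 nearest-neighbour matching in random order. Ranges cover either cohort being the treated one. Residual means the difference in mean score after matching, in within-cohort SDs.

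| d | c | Included at 0.2 SD | Residual at 0.2 SD | Caliper needed for 80% | Residual at that caliper |
|---|---|---|---|---|---|
| 0.3 | 0.58 | 82% | 0.001–0.005 | not triggered | unchanged |
| 0.4 | 0.61 | 79.5–79.6% | 0.002–0.006 | 0.33–0.34 SD | 0.006–0.020 |
| 0.5 | 0.64 | 76.6–76.9% | 0.003–0.008 | 0.77–0.84 SD | 0.047–0.098 |
| 0.6 | 0.66 | 73.5–74.0% | 0.004–0.009 | 1.02–1.17 SD | 0.106–0.181 |
| 0.8 | 0.71 | 67.0–67.7% | 0.007–0.011 | 1.35–1.63 SD | 0.256–0.359 |

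Runs set at c = 0.65 gave about 1.0–1.2 SD with residual 0.09–0.15, and at c = 0.70 about 1.4–1.6 SD with residual 0.23–0.35. A repeat with other random draws came out slightly lower (0.9–1.0 SD with 0.07–0.13, and 1.3–1.5 SD with 0.21–0.30), so these are orders of size.

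**Share of the initial difference that returns.** At d = 0.5: 0.047/0.5 = 9% to 0.098/0.5 = 20%. At d = 0.8: 0.256/0.8 = 32% to 0.359/0.8 = 45%.

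**Dependence on matching order.** In descending score order the rule triggers later (about d = 0.6) and needs smaller calipers: 0.23 SD at d = 0.6 and 0.41 SD at d = 0.8. The residuals after widening are no better, at 0.11–0.22 and 0.26–0.42. But in that order the 0.2 SD caliper already leaves 0.09–0.19 at d = 0.6 and 0.12–0.18 at d = 0.8, so widening adds little at d = 0.6 and roughly doubles the residual at d = 0.8.

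**The case against.** **The trigger can be read more narrowly.** Section 3.1.5 describes the excluded as participants without a similar score. A surplus member of the larger cohort whose close counterpart is already paired has a similar score but no partner. If only those with no opposite-cohort member within the caliper counted, a simulation with normal scores puts the share at 0.03–0.32% for c of 0.61–0.75, and the rule would never trigger. This reading does not fit the stopping condition, which counts participants included. It does show that the wording needs settling.

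**The ratio is inferred.** A variable or higher ratio would change the 84.2% cap. This stands as a condition on the whole point.

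**A reader might infer that even modest non-overlap forces a very wide caliper and undoes the matching.** The SAP does not support that. It gives no overlap, c-statistic or matching order. At c of 0.58 nothing happens and at 0.61 the widening is slight. Even at c of about 0.71, random-order matching at the widened caliper still removes more than half of the initial difference.

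**A reader might also infer that the plan is left without a way to handle non-overlap, or that the main result is affected.** Neither follows. Section 3.1.5 names IPTW for incomplete overlap, section 1.6 makes covariate-adjusted regression the primary analysis, balance is to be inspected, and the narrow-caliper result is still published in the supplement. The 80% target is also a prespecified compromise between internal and external validity.

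These points limit the size of the problem. They do not explain why the tolerance should depend on the difference in cohort size, or why widening has no limit.

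**Conclusion.** The point holds in a conditional form. Given 1:1 matching, it is exact that inclusion cannot exceed 84.2% and that the 20% allowance amounts to 259 members (5.0%) of the smaller cohort. It is also plain from the text that widening has no ceiling and no balance condition.

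The harm depends on separation the SAP does not report. It is nil or trivial up to a c-statistic of about 0.61. At an assumed c of about 0.65 to 0.70, with normal scores and random-order matching, the caliper can rise from 0.2 to roughly 1.0–1.6 SD, and the residual standardised difference from about 0.01 to about 0.09–0.35. Imbalance returns in part, not in full. The contrast with the 0.2 SD result is smaller if matching is done in descending score order.

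The effect is confined to the matched sensitivity analysis. The primary regression and IPTW are untouched. The change is still worth making, because the rule as written can put the less balanced matched estimate in the main report and the better-balanced one in the supplement.

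**What to change.** State the matching ratio in section 3.1.5, then do one of the following:

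- Define the 20% limit on the smaller (matchable) cohort. Widening would then start only if more than 0.2 × 5197 = 1039 of its members were unmatched, that is, below 4158 pairs or 8316 / 12,344 = 67.4% of the total. Under the assumptions above, that point is reached near c = 0.71.
- Keep the 0.2 SD caliper as the reported matched analysis and put any widened-caliper result in the supplement.

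The first option alone still leaves widening open-ended, so it would be stronger with a stated maximum standardised difference at which widening stops. Stating the matching order would also help.

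The cost is SAP wording and a somewhat smaller, less representative matched sample. On the plan's SD of 10 days and a simple two-group comparison, the detectable difference at 4938 pairs is 2.802 × 10 × √(2/4938) = 0.56 day. At 4158 pairs it is 2.802 × 10 × √(2/4158) = 0.61 day.
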